We propose a prospective, open-label, single-arm pilot study treating 40 subjects to assess the hypothesis that P2Y12 inhibition with Brilinta/ticagrelor (90 mg PO twice a day) reduces episodic and/or chronic migraine headache symptoms in patients with right to left shunt. There will be no randomization or blinding of therapy. The study drug will be provided, free of charge, by the manufacturer, Astra-Zeneca. All subjects will be treated with the same medical regimen, and will be treated at Columbia University Medical Center or one of Principal Investigators external offices. All subjects will have an initial visit that will include the completion of a screening questionnaire (inclusion/exclusion criteria), informed consent, transcranial Doppler screening, laboratory blood testing by venipuncture (approximately 15 cc of blood = 1 tablespoon), and instruction on the use of the daily headache log (see Appendix 1, Appendix 2). Over the next 28 days, the subjects will receive an e-mail/text reminder daily with a link to complete the headache log (see below). At a second study visit, following completion of the first baseline month, the study staff will review the subject's headache log material, will release those subjects with insufficient headache days in the screening month, will assign the remaining/eligible subjects to either the episodic or chronic migraine cohort, will distribute the study drug, will administer the Brilinta/ticagrelor loading dose, and will review the medication's proper use. After 7 days of treatment with Brilinta/ticagrelor, while still on therapy, subjects will be sent for additional laboratory testing (PRU test < 10 cc of blood by venipuncture). At the completion of the 28 days (+7 days) on Brilinta/ticagrelor, each subject will have a follow-up study visit within 7 days, before discontinuing medication. At the third study visit, headache logs will be reviewed with the study staff, results will be discussed, remaining medications and empty bottles will be returned, and adverse events will be reviewed. Headache frequency while on Brilinta/ticagrelor will be compared with the documented baseline for each subject. If the Brilinta/ticagrelor therapy was effective (> 50% reduction in monthly headache days), the subject could elect to continue therapy for an additional two months, while continuing to complete daily headache logs.

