Data collected from these 40 subjects will be evaluated to assess the feasibility of conducting a randomized, placebo-controlled, double blinded study in this population.

TRACTOR Migraine Trial Definitions

Headache Definitions:

(From: the International Classification of Headache Disorders (ICHD-II)
<http://www.ihd-classification.org/en/>)

- **Migraine without aura:** Requires all of the following symptoms: a) recurrent headaches (at least 5 lifetime attacks); b) untreated or unsuccessfully treated headache duration of 4 to 72 h; and c) at least two of the following pain characteristics: unilateral, pulsating, moderate or severe intensity, or aggravated by routine physical activity. In addition, the migraine attacks are associated with at least one of nausea/vomiting, photophobia, or phonophobia. Finally, other causes of headache must be excluded.
- **Migraine with aura:** Recurrent disorder manifesting in attacks of reversible focal neurological symptoms that usually develop gradually over 5-20 minutes and last

for less than 60 minutes. Headache with the features of migraine without aura usually follows the aura symptoms. Less commonly, headache lacks migrainous features or is completely absent.

- **Acephalic Migraine:** Migraine aura without subsequent head pain.
- **Episodic migraine:** migraine headaches as defined above, with history of 0 to 14 headache days per month.
- **Chronic migraine:** migraine headaches as defined above, with history of 15 or more headache days per month.

Adverse Events Definitions:

- **Adverse Event:** Any symptom, sign, illness or experience that develops or worsens in severity during the course of the study including intercurrent illnesses or injuries, whether or not it is considered therapy related. Adverse events will be reviewed by the Principal Investigator and the Executive Committee and will be defined as serious, or non-serious. Any adverse event will be considered “study-related” if it occurs in the time between the first dose of the study medication and 30 days after the last dose of the medication.
- **Serious Adverse Event:** Any adverse event that:
 - is fatal
 - is life-threatening requiring immediate intervention
 - requires or prolongs existing hospital stay
 - results in persistent or significant disability or incapacitation
 - requires intervention to prevent the above and/or permanent impairment or damage

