Treatment Phase (Phase 2): The subject will return for a follow-up visit to receive her/his medication within 1 week of completing the 28 day headache log. A loading dose of Brilinta/ticagrelor 180 mg will be administered in the office. Thereafter, for 28-35 days, a Brilinta/ticagrelor 90 mg tablet will be taken once in the morning and once in the evening, as close to 12 hours apart as possible. Each day, the subject will receive a text message reminder to login to the website, to record her/his headache activity. If she/he fails to login for two consecutive days, the study coordinator will place a follow-up phone call. PRU testing will be done a minimum of 7 days after the initiation of treatment, but before the medication is completed. A follow-up visit will be arranged between day 28 and day 35 days of monitoring to review efficacy, compliance, and side effects, to return unused medication, and to allow continued access to Brilinta/ticagrelor if indicated. A second Quality of Life survey will be completed.

Continued Access Phase (Phase 3): If the subject has a beneficial response to the Brilinta/ticagrelor (> 50% reduction in the average number of monthly headache days compared with the baseline), she/he will be offered continued access to the medication to complete an additional 2 months of therapy with on-going headache monitoring. A final office visit and Quality of Life Survey will be completed within 7 days of the 56th day of Phase 3 for return of unused medication, empty medication bottles and discussion about future therapeutic options. If the subject fails to have a beneficial response following the first month of treatment (Phase 2), the medication will be discontinued and participation in the study will be completed. If the subject elects to discontinue the Brilinta/ticagrelor, despite a beneficial response, participation in the study will be completed.

Outcomes Assessment/Statistical Analysis

Information from this study will be assessed to determine the feasibility of performing a larger randomized, blinded, placebo-controlled multi-center trial. We will assess not only our therapeutic drug response rate in order to estimate a required sample size for the future trial, but also our ability to recruit patients from local referring sources to estimate the time frame of such a trial. Subject compliance rate with use of daily online questionnaires will be determined. Drop-out rates, related to medication side effects will also be assessed.

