Any SAE that is unexpected and for which there is a reasonable possibility that the drug caused the adverse event will be considered a "Suspected Unexpected Serious Adverse Reaction (SUSAR), and will be reported to the FDA in accordance with 21 CFR 312.32. This report will be submitted to the FDA as soon as possible, but no later than 15 calendar days from participant notification, and unexpected fatal or life-threatening serious adverse reactions (SARs) will be submitted no later than 7 calendar days from the initial notification. Events that are considered to be "Unanticipated Problems" or UPs, will be submitted promptly to CUMC IRB, but no later than 7 calendar days following the occurrence of the UP or first knowledge of the UP.

All Serious Adverse Event reports will be reviewed/adjudicated by the Executive Committee with reporting to the IRB/FDA as required. The Principal Investigator will be responsible for the dissemination of all serious adverse event (SAE) information to each of the study investigators.

Adverse Event Reporting forms will be used to identify and track each Adverse Event during the study. The form will capture the nature of the event (e.g. Bleeding, Shortness of Breath, etc.), the likelihood that the AE was related to the study medication, the need for treatment related to the AE, the type of treatment required, and the clinical outcome of the AE. Each AE will be classified as an anticipated or unanticipated issue with the study medication. Any bleeding AE will be further characterized (separate report form) as a major life-threatening bleed, major non-life threatening bleed or minor bleed. Additional separate report forms are available in the event of a subject mortality during the study. All AE's will be reported as safety endpoints in the final study report.

If a participant, or the female partner of a male participant should become pregnant during the study (with or without an adverse event), the pregnancy will be followed to delivery (no matter how the pregnancy ends, spontaneous abortion, elective abortion, pre or term delivery etc.) and the outcome of the pregnancy will be documented and reported as appropriate (to both FDA and to AstraZeneca). Any congenital anomaly or birth defect, in the offspring of a patient (male or female) who was taking the study drug when pregnancy occurred, will be reported to the IRB, to the FDA and to AstraZeneca as an SAE.

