Appendix 1:

Trial Schedule: (see attached TRACTOR Migraine Trial Flow Sheet in Appendix 2)

Study Visit #1: At the time of the first visit, study coordinator/investigators will discuss trial and subject eligibility for participation based on migraine headache frequency. The coordinator will collect all demographic information required for the study. Participant will receive explanation of the additional testing required for trial participation. After patient has been given an opportunity to ask questions, a screening consent will be signed to perform this testing. Participant will receive a Patient Study Number. Transcranial Doppler study will be performed. If negative for right to left shunt, participant will be sent back to the referring physician for on-going clinical care. If positive for right to left shunt (Spencer Grade ≥ 2) participant will be eligible to continue in the trial. The trial will be explained in detail, including participant responsibilities, and the patient will receive written study materials. A complete TRACTOR Migraine Headache Trial consent will be signed. The participant will receive a test e-mail/text message and must demonstrate the ability to answer the headache log questions. A Quality of Life Survey will be taken. Laboratory screening is done. End of visit.

Study Phase 1:
(28 Days) Within 72 hours of the laboratory evaluation, participant will be notified of results of laboratory testing and ability to continue participation. She/he will begin to receive daily reminders (e-mail/text message) to log-in to answer the headache log questions. A follow-up appointment will be scheduled within 7 days of the completion of 28 days of headache monitoring.

Study Day 29: Headache log entries will be reviewed by the Study Coordinator to determine final eligibility for trial based on the number of headache days documented.

Study Visit #2: Must occur within seven days of completion of baseline headache log. Participant will return to receive her/his medication. She/he will receive a loading dose of 180 mg of Brilinta/ticagrelor and an additional 70 tablets and will again review the responsibilities for participation with the coordinator. The participant will be observed for 30 minutes after taking the first medication dose.

Study Phase 2:

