(28-35 Days) Participant will receive reminder text message/e-mail to take daily study medication, and to log-in to answer the headache log questions. Participant will take Brilinta/ticagrelor 90 mg twice daily for 28-35 days. Participant will receive instructions for PRU testing.

PRU Testing: (> 7 days on drug)	Participant will go to local laboratory or to study center for blood testing of platelet inhibition.
Study Visit #3:	Within 7 days of completion the 28 th day of the study medication participant will return to meet with the study coordinator to review the results of the therapy, to return unused medication, and to review any adverse events. If no perceived benefit, participation is completed. If subject has had a clinical benefit, options for on-going therapy with additional headache log entries will be discussed. Participant will complete a follow-up Quality of Life questionnaire.
Continued Access (56-63 days):	If eligible, participant will continue to take Brilinta/ticagrelor for an additional 2 months. She/he will continue to receive daily e-mail/text message reminders to log-in to record headache data.
Study Visit #4:	Within 7 days of the 56 th day of study medication, participant will return to meet with the study coordinator to review the results of the therapy, to return unused medication, and to review any adverse events. Participant will complete a follow-up Quality of life questionnaire. Study is complete.

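### Adverse events count as study-related until 30 days after the last dose, but no contact is scheduled after Visit 3 or Visit 4, so later events in ordinary completers are captured only if volunteered

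*Combined protocol and SAP*

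**What the plan says.** Under Adverse Events Definitions, an event is study-related if "it occurs in the time between the first dose of the study medication and 30 days after the last dose of the medication". Under Reporting of Serious Adverse Events, the plan adds: "All AE's will be reported as safety endpoints in the final study report".

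The end of contact is set as follows.

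- **Visit 3.** Study Design and Statistical Procedures places it on drug: "each subject will have a follow-up study visit within 7 days, before discontinuing medication".
- **Subjects without a beneficial response.** Under Continued Access Phase (Phase 3), "the medication will be discontinued and participation in the study will be completed".
- **Responders who choose to stop.** Same section: "If the subject elects to discontinue the Brilinta/ticagrelor, despite a beneficial response, participation in the study will be completed".
- **Subjects in continued access.** Appendix 1, Study Visit #4: "Participant will complete a follow-up Quality of life questionnaire. Study is complete".

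The flow chart in Appendix 2 has no column after Visit 4. Two provisions reach further: pregnancies are followed to their outcome (Reporting of Serious Adverse Events), and a subject withdrawn because of an adverse event has a follow-up assessment (Withdrawal of Subjects). Neither applies to a subject who finishes as planned.

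**The concern.** A period in which events count is useful only if someone asks about events throughout it. Here the definition runs 30 days past dosing, while the last planned enquiry falls on or close to the last day of dosing. Whether an event on, say, post-dose day 10 reaches the database depends on the former subject making contact. Staff also have no clear rule for it: the first sentence of the same definition confines adverse events to those arising while the study is under way, and for this person participation is already over.

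What is at stake is the overall listing of adverse events and serious adverse events. The plan notes under Potential Risks that no use of the drug in migraine has been reported before, and under Other Potential Risks that outcomes will be set against historical data to detect new or unexpected events. With 40 treated subjects, a few unrecorded events would visibly change what is reported.

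**Working it through.** The plan states no figure for safety coverage, so there is none to reproduce.

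**Inputs**

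- Post-dose part of the window: 30 days (Adverse Events Definitions).
- Phase 2 exposure: "Participant will take Brilinta/ticagrelor 90 mg twice daily for 28-35 days" (Appendix 1). Check against supply: "an additional 70 tablets" at 2 per day is 70/2 = 35 days, which matches the upper limit.
- Continued access: 56 to 63 days (Appendix 2). Total exposure is therefore 28 + 56 = 84 to 35 + 63 = 98 days.

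**Formula.** Share of the window without scheduled contact = post-dose days not covered / (days on drug + 30).

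| Subject | Days on drug | Window | Share without contact |
|---|---|---|---|
| Stops at Visit 3 | 28 | 58 | 30/58 = 51.7% |
| Stops at Visit 3 | 35 | 65 | 30/65 = 46.2% |
| Completes continued access | 84 | 114 | 30/114 = 26.3% |
| Completes continued access | 98 | 128 | 30/128 = 23.4% |

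**Visit 4 after the last dose.** The text is explicit that Visit 3 is on drug. For Visit 4 this is only inferred, from the 56–63 day phase and the return of unused drug. If dosing stopped on day 56 of Phase 3 and the visit came 7 days later, 7 post-dose days would be seen and 23 would not. With 28 + 56 = 84 days on drug the share is 23/114 = 20.2%; with 35 + 56 = 91 days it is 23/121 = 19.0%. The range for continued access is therefore about 19–26%.

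**Visit 3 after the last dose.** The same allowance there would give 23/58 = 39.7%, but the design section does not permit it.

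**All 40 subjects together.** This depends on the proportion who continue, which the plan does not give. Taking 50% as an assumption, with Visit 4 on drug: 40 × 30 / (20 × 58 + 20 × 114) = 1200/3440 = 34.9% at the shorter exposures, and 1200 / (20 × 65 + 20 × 128) = 1200/3860 = 31.1% at the longer. The same sum gives 37–42% if 25% continue and 27–31% if 70% continue.

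**The stated safety periods side by side**

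| Place | Period |
|---|---|
| Adverse Events Definitions | first dose to 30 days after the last |
| Primary Study Endpoints (safety) | on drug |
| Statistical Considerations and Analysis Plan | three-month treatment period |
| Appendix 2 | contacts end at Visit 3 or Visit 4 |

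The first does not agree with the others. The third fits only subjects who enter continued access.

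**The case against.** The strongest reply is that the 30-day sentence is a rule of attribution, not a promise of surveillance. It says when an event is regarded as study-related. The named safety endpoints are tied to treatment: the primary one to time on drug, the analysis plan's to the treatment period. On this view the definition merely needs tidying in a descriptive pilot. Much of this stands. The primary safety endpoint is not affected, which limits the weight of the point. But attribution to a period in which nobody asks has little content, and the plan does undertake to report all adverse events.

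Four stronger readings are tempting, and the documents do not support them.

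- **That up to half of the safety information is lost.** The percentages count calendar days. The plan gives no risk per day after dosing, and Dose Rationale and Risk/Benefits describes reversible binding, so equal risk on and off drug cannot be assumed.
- **That post-dose events can never be seen.** The coordinator is the central contact for adverse events (Monitoring Plan), so spontaneous reports remain possible. What is missing is a scheduled enquiry.
- **That the gap biases a comparison of subjects who stop with those who continue.** The uncovered time is 30 days or slightly less in either group. The share differs because continuers have about three times the exposure in the denominator (84–98 against 28–35 days). That difference alone makes raw counts non-comparable, a later call would not remove it, and no such comparison is planned.
- **That the report will give a rate over the full window.** No section plans one; the results are described as descriptive only.

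**Conclusion.** The point holds as a mismatch between definition and schedule. As written, the plan cannot ascertain adverse events over the period it calls study-related. For ordinary completers, 46–52% of the days in that period have no scheduled contact if they stop at Visit 3, and about 19–26% if they complete continued access. The first range rests on explicit text. The second depends on whether Visit 4 falls on or up to 7 days after the last dose.

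The consequence is confined to overall reporting of adverse events and serious adverse events. It is worth correcting because safety in a new population is a stated interest of the study and the remedy is cheap. It does not undermine the primary safety endpoint.

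**What to change.** Reconcile the safety periods in Adverse Events Definitions, Primary Study Endpoints, Statistical Considerations and Analysis Plan, and Appendix 2, then do one of the following.

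- **(a) Add a contact.** Send every dosed subject who has not withdrawn consent one adverse-event-only REDCap link, or have the coordinator call, 30 days after the recorded last dose. Show it as a column in Appendix 2. Scheduled contact would then reach day 58–65 after first dose, or day 114–128 after continued access, and the uncovered share falls to zero for subjects who respond. The recall period is similar to the 28–35 days between Visits 2 and 3 that the plan already accepts. The rule in Withdrawal of Subjects that data collection stops after a medical withdrawal would need a matching exception.
- **(b) Narrow the tables.** If no contact is added, limit the adverse-event tables to events up to the last scheduled visit, label them on-treatment, and list later spontaneous reports separately.

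Under (a), the end of participation should not simply be moved to the new contact. Contraception and unchanged headache medication are required for the duration of the study, so a later end date would prolong both by about 30 days. State that the contact is for adverse events only and leave those obligations, and the headache logs, to the existing text.

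Option (a) costs about 40 short contacts through the existing survey system or coordinator, plus the schedule change. Option (b) costs only wording, but leaves the post-dose period without enquiry. Option (a) is preferable because it makes the stated period observable.
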